	
 12. Adequate inflow to the target lesion(s) involving at least a patent femoral or deep femoral vein and a landing zone in the CFV free from significant disease requiring treatment 13. Reference vessel diameter is of adequate size to accommodate the appropriate size stent as measured by IVUS 14. All vessels from insertion site through target vessel can accommodate a 9F or 10F sheath, depending on the stent size used 15. Ability to cross interventional devices through target lesion(s) 16. In DVT subjects, successful treatment of acute thrombus must have occurred prior to receiving any DUO Stents for an underlying obstructive lesion. Successful treatment of acute thrombus is defined as reestablishment of antegrade flow with $\leq 30\%$ residual thrombus (confirmed by venogram or IVUS) and freedom from bleeding and symptomatic pulmonary embolism (confirmed by imaging). After successful treatment of thrombus is confirmed, eligible obstructive lesion(s) can be treated with a DUO Stent during the same procedure. 17. All subjects must undergo a SARS-CoV-2 test and have a negative test result within 8 days prior to the index procedure. If a SARS-CoV-2 test is unavailable due to institution policy, a test shortage, or if there is a delay in test results, the subject must complete the COVID-19 questionnaire and must have answered NO to all questions to be eligible for enrollment. A SARS-CoV-2 test will not be required for enrollment if a subject has received a complete cycle of an authorized COVID-19 vaccine or has documented evidence of a positive COVID-19 antibody test and is asymptomatic and has no long-lasting effects (per PI discretion) from a prior COVID-19 infection. 18. A measured temperature less than 99.5°F (37.5°C) on the day of the index procedure and no history of fever or feeling feverish within 14 days of the index procedure 19. No prior history, within 60 days of the index procedure, of a SARS-CoV-2 positive test, or COVID-19 symptoms

Exclusion Criteria:
	
 1. Target limb symptoms caused by peripheral arterial disease 2. Presence of unresolved significant PE prior to use of the DUO Venous Stent System confirmed by chest CT. If subject has documented history of significant pulmonary embolism within the last 6 months, a chest CT is required to confirm significant pulmonary embolism is not currently present.

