19.2. Analysis Groups

A subject is defined as ITT and officially enrolled in the study once the DUO Venous Stent System is advanced through the introducer sheath.

Subjects in whom no DUO Stent implant is placed will be exited after 30 days. Subjects in whom at least one DUO Stent implant is placed will be followed for 36 months.

The full analysis set (FAS) are subjects who meet the ITT definition and have data evaluable for the primary endpoints.

The PP population will be defined as ITT subjects with evaluable data that have met the definition for device success, excluding subjects meeting criteria for a protocol violation(s) as outlined in **Section 17.8** and as determined by the Sponsor.

In addition, a SARS-CoV-2 positive population will be defined as:

1. Any documented confirmation of a SARS-CoV-2 positive test result or SARS-CoV-2 positive antibody test (at any approved testing site) from screening through study exit. Subjects will be grouped according to when they became SARS-CoV-2 positive based on the date that testing was performed as compared to the index procedure (i.e., within 30 days, greater than 30 days but within 12 months, greater than 12 months).
2. In the absence of a SARS-CoV-2 test, subjects will be required to complete a COVID-19 questionnaire. Any subject that completes a questionnaire after screening and answers YES to any question on the questionnaire will be included in the SARS-CoV-2 positive population.
3. Regardless of SARS-CoV-2 status or COVID-19 questionnaire results, all adverse events will be assessed by the PI for relatedness to a possible COVID-19 infection by indicating YES, NO, or UNKNOWN.

Any subject that has an adverse event where the PI indicates YES for relatedness will be included in the SARS-CoV-2 positive group.

Due to the unknown but possible risks associated with COVID-19 and hypercoagulability, once a subject is placed in the SARS-CoV-2 positive population, they will remain there regardless of future SARS-CoV-2 test results and or vaccination status. Any subject not meeting the above criteria will be placed in the SARS-CoV-2 Negative population.

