19.4. Study Success

The study will be considered a success if the primary safety endpoint is met in either the SARS-CoV-2 negative subset or all subjects and the primary efficacy endpoint is met in either the SARS-CoV-2 negative subset or all subjects. The Type I error for testing in both the SARS-CoV-2 negative subset and all subjects will be controlled using the Hochberg correction.

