19.7. Handling of Missing Data

A sensitivity analysis to the missing data in the ITT sample will be conducted for both the primary safety and efficacy endpoints in the SARS-CoV-2 negative subset and all subjects. The sensitivity analysis will include a best case, worst case and tipping point analysis. The best-case analysis will impute successes for the missing data. The worst-case analysis will impute failures for missing data. The tipping point analysis starts with the best-case analysis and continues until the worst-case analysis is completed, by increasing the number of missing cases imputed as failures by one in each analysis. The goal of the tipping point analysis is to determine at what point the imputation of

failures causes the statistical evaluation of the endpoint to lose statistical significance. If the worst-case analysis maintains statistical significance, the tipping point analysis is not necessary.

19.8. **Summary of Baseline Demographics, Index Procedure Measurements, and Subject Compliance**

Baseline demographics including at a minimum gender, age, and selected medical history will be summarized for ITT subjects overall and in the SARS-CoV-2 – negative subset for primary safety and for primary efficacy. In addition, angiographic characteristics and measurements, as well as procedure characteristics will be summarized.

Subject follow-up and compliance with the protocol will be reported. The number and percent of subjects enrolled, completing study-required follow-ups, and completing the study will be summarized. The subjects who exit the study early will be summarized along with the reason for early study termination.

19.9. **COVID-19 Statistical Considerations**

Given that COVID-19 has been associated with a hypercoagulable state which has the potential to increase MAE occurrence and decrease patency, the study has been modified to test the primary safety and effectiveness hypotheses in both the SARS-CoV-2 negative subset and all subjects (regardless of SARS-CoV-2 status).

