The performance goals for both primary safety and primary effectiveness were established based on research in a pre-COVID-19 era and therefore do not account for potential increases in MAEs or decreases in patency associated with SARS-CoV-2 or COVID-19. For each of the hypothesis tests, the current plan is to use the same performance goal in all subjects and in the SARS-CoV-2 negative subgroup given that the potential effects due to SARS-CoV-2 are not well understood. This decision will be revisited prior to analysis of the study data. In the event that additional information becomes publicly available regarding SARS-CoV-2, as related to the VIVID study primary endpoints, we may summarize the major event rate and primary patency in the subject population without and with SARS-CoV-2, and if possible, further based on the extent of COVID-19 illness. Should this information suggest that it may be reasonable to lower the performance goal for the all subject cohort, negotiation with FDA will be pursued given the FDA guidance document, “Statistical Considerations for Clinical Trials During the COVID-19 Public Health Emergency” dated June 2020.

19.10. **Primary Safety Objective**

Subjects Included the Analysis: Subjects who meet the ITT definition.

Endpoint: The primary safety endpoint is freedom from major adverse events (MAEs) at 30 days post index procedure evaluated per subject. MAEs are defined in **Section 6.1** Primary Endpoints.

Performance Goal: Disease state specific PGs were calculated from the point estimates for major bleeding, pulmonary embolism and peri-procedural mortality from Razavi et al¹ converted to freedom from estimates and application of a 10% non-inferiority margin. For example, the expected freedom from the combined primary safety event for nonthrombotic subjects is $100 - (0.3 + 0.2 + 0.1) = 99.4\%$. Therefore, the PG for the nonthrombotic group is $99 - 10 = 89\%$. The same calculation for the acute-thrombotic group results in an 87% PG, $87\% = 100 - (1.1 + 0.9 + 0.7) - 10$. Lastly, the PG for chronic postthrombotic is $88\% = 100 - (0.9 + 0.6 + 0.3) - 10$. Given the similarity of the disease-state specific PGs, it was determined that a disease state specific goal was not necessary. A PG of 89% was adopted for the study in both the SARS-CoV-2 negative subset and overall.

Hypothesis and Performance Goal:

H₀: Proportion of subjects with freedom from MAE (p_{MAE}) is less than or equal to the (PG) at 30 days, $p_{MAE} \leq 89\%$

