H₁: Proportion of subjects with freedom from MAE is greater than the (PG) at 30 days, $p_{MAE} > 89\%$

The freedom from MAE proportion will be calculated such that the numerator is the number of subjects in whom a MAE did not occur within 30 days of the index procedure. The denominator is the number of subjects with 30 days of follow-up plus the number of subjects with a MAE prior to 30 days who exited the study prior to 30 days, if any.

Sample Size Rationale: Using PASS 19, a one-sample Exact Test (binomial enumeration), power = 90%, one-sided Type I error controlled at 2.5%, and assumed freedom from MAE of 96.1% with a PG goal of 89%, the required evaluable sample size is 140 subjects.

Primary Statistical Analysis: The primary statistical analysis will be conducted in the FAS subset for the primary safety endpoint overall and in the SARS-CoV-2 negative subset. The primary statistical method is a one-sample exact test comparing the proportion of subjects free from a MAE to the PG using a two-sided $\alpha = 0.05$. The exact two-sided 95% confidence interval for the proportion of subjects free from MAE will be calculated.

The two-sided p-value in the SARS-CoV-2 negative subgroup and all subjects will be calculated and ordered from largest to smallest. If the largest p-value, is statistically significant at $p < 0.05$ then the hypothesis test is statistically significant in both the SARS-CoV-2 negative subset and all subjects. If not, testing continues to the smallest p-value. If the smallest p-value < 0.025 then the hypothesis test is statistically significant in the group for which the smallest p-value is associated with. If the

¹ Razavi MK, Jaff MR, Miller LE. Safety and Effectiveness of Stent Placement for Iliofemoral Venous Outflow Obstruction Systematic Review and Meta-Analysis. Circ Cardiovasc Interv. 2015;8:e002772. DOI: 10.1161/CIRCINTERVENTIONS.115.002772.)

smallest p-value ≥ 0.025 , then the hypothesis test is not statistically significant in either the SARS-CoV-2 negative subset nor all subjects.

Additional Analysis: The evaluation for pooling analyses specified in **Section 19.6** will be completed. If there is missing data for the ITT subjects, the sensitivity to missing data analysis outlined in **Section 19.7** will be completed. Additionally, the primary statistical analysis will be conducted in the per protocol sample overall and in the SARS-CoV-2 negative subset.

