Sample Size Rationale: With an expected FAS sample size of N=128, one-sided Type I error less than or equal to 2.5%, and assumed primary patency at 12 months equal to .96, .87, .79, i.e. the point estimates for primary patency from Razavi et al for nonthrombotic, acute thrombotic, and chronic postthrombotic respectively, the power for primary efficacy ranges from 96 – 99% depending on proportion in each disease-state given a minimum of at least 20% in each group. The table below provides the matrix of simulated power varying the ITT proportions for the disease states.

Power Calculations Using Simulation for the Primary Statistical Analysis

Proportion of Subjects Expected in Each Group			Assumed Freedom from Primary Efficacy				Calculated Performance Goal				Power at N=128 Evaluable (20% attrition for N=160 enrolled)
NT	AT	CPT	NT	AT	CPT	Pooled	NT	AT	CPT	PG	One-sided Type I error = 2.5%
0.3333	0.3333	0.3333	0.96	0.87	0.79	0.873	0.83	0.7	0.66	0.73	98%
0.2	0.2	0.6	0.96	0.87	0.79	0.84	0.83	0.7	0.66	0.702	96%
0.2	0.6	0.2	0.96	0.87	0.79	0.872	0.83	0.7	0.66	0.718	99%
0.6	0.2	0.2	0.96	0.87	0.79	0.908	0.83	0.7	0.66	0.77	96%
0.3	0.3	0.4	0.96	0.87	0.79	0.865	0.83	0.7	0.66	0.723	97%
0.3	0.4	0.3	0.96	0.87	0.79	0.873	0.83	0.7	0.66	0.727	99%
0.4	0.3	0.3	0.96	0.87	0.79	0.882	0.83	0.7	0.66	0.74	98%
0.4	0.4	0.2	0.96	0.87	0.79	0.89	0.83	0.7	0.66	0.744	99%
0.4	0.2	0.4	0.96	0.87	0.79	0.874	0.83	0.7	0.66	0.736	98%
0.2	0.4	0.4	0.96	0.87	0.79	0.856	0.83	0.7	0.66	0.71	98%

Primary Statistical Analysis: The primary statistical analysis will be conducted in the FAS subjects overall and in the SARS-CoV-2 negative subgroup. The primary statistical comparison will use a one-sample Z-test comparing the proportion of subjects with primary patency to the PG using a one-sided $\alpha = 0.025$ equivalent to a z-score of 1.96. The variation in the proportion will be estimated using the disease-specific performance goals themselves, i.e. under the null, rather than use the estimated patency rates, i.e. under the alternative.

The estimates that will be observed for primary patency in each disease etiology are noted as follows:

$\hat{p}_{p_pat_NT}$ = The primary patency observed in the NT subjects.
 $\hat{p}_{p_pat_AT}$ = The primary patency observed in the AT subjects.
 $\hat{p}_{p_pat_CPT}$ = The primary patency observed in the CPT subjects.

The percent of subjects in the FAS with each disease etiology are noted as follows:

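### The stated 90% safety power belongs to a single all-subjects test; at 140 evaluable the plan's Hochberg rule gives 82–86% if positives and negatives share the 96.1% rate and at least one subject is SARS-CoV-2 positive

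*Combined protocol and SAP*

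**What the plan says.** The Sample Size Rationale in section 19.10 uses a one-sample exact binomial test with "power = 90%, one-sided Type I error controlled at 2.5%, and assumed freedom from MAE of 96.1% with a PG goal of 89" (per cent), and arrives at 140 evaluable subjects. Section 19.3 divides by 0.875 to reach 160 enrolled.

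The test that decides success is different. Section 19.9 states that "the study has been modified to test the primary safety and effectiveness hypotheses in both the SARS-CoV-2 negative subset and all subjects", and section 19.4 that "The Type I error for testing in both the SARS-CoV-2 negative subset and all subjects will be controlled using the Hochberg correction". Section 19.4 counts safety as met if it is met in either population. Section 19.10 gives the steps. If the larger two-sided p-value is below 0.05, both populations are significant. Otherwise: "If the smallest p-value < 0.025 then the hypothesis test is statistically significant in the group for which the smallest p-value is associated with". The same 89% goal applies to both populations.

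The plan provides for positive subjects. Inclusion criterion 17 waives the SARS-CoV-2 test for subjects with "documented evidence of a positive COVID-19 antibody test and is asymptomatic", subject to its other conditions. Section 19.2 places a subject in the positive population on any documented positive test or "SARS-CoV-2 positive antibody test (at any approved testing site) from screening through study exit", and that status is permanent. Section 19.9 concedes that "the potential effects due to SARS-CoV-2 are not well understood". No section states an expected number of positives, a rate in positives, or power for the two-population rule.

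For efficacy, section 19.11 says: "The table below provides the matrix of simulated power varying the ITT proportions for the disease states". Those figures are also for one test in all subjects.

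**The concern.** A power statement should describe the rule by which the endpoint is won or lost. Here the hypotheses were changed to cover two nested populations, but the sizing paragraph still spends the full one-sided 2.5% on a single test. Under Hochberg, the all-subjects result can stand alone only at one-sided 1.25%. At 2.5% it counts only if the negative subset also passes. If the negative subset adds little chance of its own, the rule is harder to satisfy than the test that was powered.

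At stake is the planned risk of missing the safety endpoint, one of two that must both be met. It is stated as about 10% and would be 14–18% in the equal-rate case. The plan also does not say whether 96.1% is the rate in all subjects or in negatives, and that choice can change even the direction of the difference.

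**Working it through.** **Inputs from the plan.** Goal 0.89, assumed rate 0.961, n = 140 evaluable, one-sided 0.025 (sections 19.10 and 19.3); Hochberg thresholds of two-sided 0.05 and 0.025 (section 19.10). I take the two-sided exact p as twice the one-sided p, so the thresholds are one-sided 0.025 and 0.0125.

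**Assumptions, not in the plan.** The number of negatives m and the MAE-free rate in positives.

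**1. Reproducing the plan's figure.** Let T be the number of subjects with an MAE among 140. Under the goal, T ~ Bin(140, 0.11):
- P(T ≤ 8) = 0.0240 and P(T ≤ 7) = 0.0106.
- One-sided 0.025 therefore allows 8 failures. Power = P(T ≤ 8) with T ~ Bin(140, 0.039) = 0.902.
- One-sided 0.0125 allows 7 failures. Power = P(T ≤ 7) = 0.818.

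The stated 90% is right for the single test. Enrolment also reproduces: 140/0.875 = 160.

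**2. Power of the Hochberg rule.** Let X ~ Bin(m, 1 − p_neg) be failures in negatives and Y ~ Bin(140 − m, 1 − p_pos) failures in positives, independent, with T = X + Y. Success occurs if both one-sided p-values are ≤ 0.025 or either is ≤ 0.0125. I enumerated all (X, Y).

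Worked case, m = 112 (20% positive), 0.961 in everyone. The negatives pass 0.025 with at most 5 failures and 0.0125 with at most 4.
- P(T ≤ 7) = 0.8182
- T = 8 and the negatives pass = 0.0166
- T > 8 and the negatives pass 0.0125 = 0.0009
- Total = 0.8357

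The single test keeps all of P(T = 8) = 0.902 − 0.818 = 0.084. Hochberg keeps only the part in which the negatives also pass.

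**3. Results at n = 140.**

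| Case | Hochberg | Single test |
|---|---|---|
| No positives | 90.2% | 90.2% |
| 96.1% in everyone, m = 139 (minimum over 70–139) | 82.3% | 90.2% |
| 96.1% in everyone, m = 128 (maximum) | 86.3% | 90.2% |
| 96.1% in everyone, m = 126 | 83.6% | 90.2% |
| 96.1% in everyone, m = 112 | 83.6% | 90.2% |
| 96.1% in everyone, m = 98 | 83.5% | 90.2% |
| Negatives 96.1%, 20% positive at 93% | 76.6% | 81.6% |
| Negatives 96.1%, 20% positive at 89% | 68.8% | 67.2% |

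Over every m from 1 to 139 with equal rates the range is 81.8–86.3%. The minimum-likelihood two-sided exact p raises only the top, to 86.6%. In the last two rows most of the fall comes from the lower overall rate, not from Hochberg.

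Overall rate held at 96.1%, with k positives at rate p_pos and p_neg = (0.961 × 140 − p_pos × k)/(140 − k):

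| k | p_pos | p_neg | Hochberg |
|---|---|---|---|
| 14 | 0.93 | 0.9644 | 86.7% |
| 28 | 0.93 | 0.9687 | 88.0% |
| 14 | 0.90 | 0.9678 | 90.1% |
| 28 | 0.90 | 0.9762 | 93.3% |

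**4. Other evaluable numbers, equal rates.**
- Averaged over n ~ Bin(160, 0.875): 81.4–83.3% for negative shares of 70–95%, against 86.7% for the single test.
- n = 152–160, every negative count from 50% up: 84.2–92.2% (single test 90.3–92.5%).
- n = 140–160, same counts: 78.7–92.2% (single test 86.3–92.5%).

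**5. Efficacy.** I simulated N = 128 with a multinomial disease mix, the goal from the row weights and the null variance of section 19.11.
- Single test, 0.2/0.2/0.6 row: 96.8% (printed 96%, consistent with truncation to a whole per cent).
- Single test, 0.6/0.2/0.2 row: 99.3% (printed 96%).
- Hochberg, equal patency, negative shares 60–95%: about 94–99%.
- Hochberg, negatives as planned and positives 5 points lower: down to 86.4% (single test 88.9%). Positives 10 points lower: down to 79.3% (single test 73.8%).
- Hochberg, overall patency held and positives 5 points lower: 95.7% or more.

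**The case against.** The quoted sentence is correct for what it names: one exact test, one alpha, one rate, one goal. Nothing is miscalculated in it. This stands; the defect is that it is the only safety power given and does not describe the deciding rule.

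The size of the loss is partly an accident of n = 140, the first n in this region to allow 8 failures. Removing a single positive leaves 139 negatives, who are allowed only 7. At n = 138, 139 and 151 the two all-subjects cut-offs coincide and Hochberg is never below the single test; at most other n the loss runs from about zero to about 8 points. This also stands, so the claim that one positive is enough should not be carried to other n. But 140 is the plan's own design point, and averaging over attrition still leaves a loss of 3.4 to 5.3 points.

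The direction is not settled. The plan added the subset because COVID-19 might raise the event rate, and if positives do worse with the overall rate held, Hochberg power straddles 90%. That is right, and it is why the result must be given as a range. It does not justify leaving the rule's power unstated.

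Finally, the shares and rates needed are unknown. A table over stated assumptions handles that, and section 19.11 already treats the unknown disease mix in the same way.

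**Conclusion.** The point holds. The 90% is single-test power in all subjects, and the plan gives no power for the Hochberg rule that decides safety. At 140 evaluable, with 96.1% in positives and negatives alike and at least one positive, the rule's power is about 82–86%, so the stated figure is 4 to 8 points too high. With no positives it is 90.2%. With the overall rate held and positives worse, the cases examined give 86.7–93.3%. If 96.1% applies only to negatives and positives do worse, power can be well below 80%, mainly because the overall rate drops. Every figure other than the no-positives case rests on shares and rates that the plan does not supply.

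The 0.6/0.2/0.2 efficacy cell is a separate, minor and conservative error. The 96–99% single-test range survives because the 0.2/0.2/0.6 row sets its lower end.

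Type I error, the decision rule and the analysis are not in question. This should be corrected, but it does not threaten the validity of the trial.

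**What to change.** - In sections 19.3, 19.10 and 19.11, label the existing power figures as single-test power in all subjects.
- In section 19.10, state whether 96.1% is the assumed rate in all subjects or in negatives.
- Add a short table of safety power under the Hochberg rule over stated negative shares, evaluable numbers and rates in positives, showing both the equal-rate and the overall-rate-held cases.
- If an efficacy Hochberg range is given, present about 94–99% at N = 128 only as conditional on equal patency and negative shares of 60–95%.
- Correct the 0.6/0.2/0.2 cell of the efficacy table to 99%.

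The cost is some text, one small table and one cell. The stated safety power becomes conditional and, with equal rates, less favourable. No change to enrolment, decision rule or analysis is asked for; whether the restated range is acceptable is for the sponsor to say.
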